6.3 End of Study Evaluations

An interval of approximately six (6) months will occur between completion of baseline and follow-up measures. Participants will be scheduled for a return visit to SJCRH within 6 months ± 4 weeks to complete a follow-up evaluation. One to two weeks prior to their scheduled follow-up visit, participants will complete objective and subjective sleep measures at home, including five days of actigraphy, daily sleep diary, and standardized sleep measures. Participants will also complete measures of health-related quality of life and psychological distress prior to returning to SJCRH. During their campus visit participants will have a visit with a medical provider, provide an interim history, undergo a neurocognitive evaluation, and have biological samples collected. If a participant is unable to return to St. Jude to complete their 6 month visit, a standardized neurocognitive questionnaire, which is also administered at baseline, along with the objective and subjective sleep measures will be mailed to them to complete at home and return. The follow-up assessment will be scheduled to occur while participants are actively taking melatonin/placebo. However, treatment with melatonin/placebo will not be extended by more than two weeks.

6.4 Long-Term Follow-up Evaluations

The study is approximately six (6) months in duration. No long-term

Revision 4.3, dated: 09-20-16

IRB Approval date: 10-11-16

Protocol document date: 09-20-16

follow-up evaluations will be performed.

7.0 EVALUATION CRITERIA

7.1 Response Criteria

Three domains of neurocognitive functioning will be evaluated as primary study outcomes 1) attention, 2) memory, and 3) executive functioning. These will be examined at the 6 month interval. The secondary outcomes will be evaluated by subjective and objective sleep parameters assessed at the 3 month and 6 month time periods.

Response in the neurocognitive functioning domains of attention, memory, and executive functioning will be documented as either 1) Improvement; 2) No change; or 3) Worsened. The same responses will be used for sleep onset latency. Correlative psychosocial measures of health-related quality of life and psychological distress will be examined at 6 months of melatonin/placebo treatment.

7.2 Toxicity Evaluation Criteria

Adverse events will be monitored and graded according to the Common Terminology Criteria for Adverse Events version 4.0 (CTCAE v4.0). A copy of the current version of the CTCAE version 4.0 can be downloaded from the CTEP home page (<http://ctep.info.nih.gov>) or from the St. Jude home page.

7.3 Acceptable Percentage of Missed Doses for Research and Standard of Care Drugs

Participant adherence to melatonin/placebo treatment will be monitored following the first week of therapy and monthly thereafter during the six month trial. Participants who reported <80% adherence will be contacted by telephone to problem-solve potential barriers to adherence and brainstorm solutions to improve adherence. A standardized problem-solving model will be utilized for this process. The participant will select one solution that he/she is willing to try over the next month and this solution will be operationalized. Participants will not be removed from the study trial due to poor adherence.

8.0 CRITERIA FOR REMOVAL FROM PROTOCOL THERAPY AND OFF-STUDY CRITERIA

8.1 Off-study Criteria

- 8.1.1 Death
- 8.1.2 Lost to follow-up
- 8.1.3 Request of the research participant
- 8.1.4 Development of unacceptable toxicity during treatment
- 8.1.5 Discretion of the Study PI, such as the following:
 - The researcher decides that continuing in the study would be harmful
 - A treatment/medication is needed that is not allowed on this study
 - New information is learned that a better treatment is available
 - The study is not in the participant's best interest
- 8.1.6 Participant develops a subsequent malignant neoplasm while on study
- 8.1.7 Participant develops a serious and/or life threatening medical condition while on study
- 8.1.8 Study evaluations are complete
- 8.1.9 Participant does not have neurocognitive impairment and no delayed sleep onset latency at baseline

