3.6 Procedures for Randomizing Research Participants

Once participants have completed baseline neurocognitive and sleep evaluations, they will be stratified into three cohorts. For stratification purposes the following definitions will apply:

- 1) **Neurocognitive impairment** will be defined as performance on at least one measure of attention, memory, and/or executive functioning ≤ 10 th

percentile. Performance will be measured using the following tests: Trail Making Test Part B, Digit Span Forward and Backward, Controlled Oral Word Association Test, California Verbal Learning Test-II (long delay free recall), and Conners' Continuous Performance Test-II (variability index).

2) **Absence of neurocognitive impairment** will be defined as performance >10 th percentile on all six measures of attention, memory, and executive functioning.

3) **Delayed sleep onset latency** will be defined as self-report of inability to fall asleep within 30 minutes \geq once a week during the past month.

4) **Absence of delayed sleep onset latency** will be defined as inability to fall asleep within 30 minutes $<$ once a week during the past month.

Each of the cohorts is described below:

Cohort 1:

- a. Has neurocognitive impairment defined as performance on at least one measure of attention, memory, and/or executive functioning ≤ 10 th percentile.
- b. Is absent of delayed sleep onset latency defined as an inability to fall asleep within 30 minutes $<$ once a week during the past month.

Cohort 2:

- a. Has neurocognitive impairment defined as performance on at least one measure of attention, memory, and/ or executive functioning ≤ 10 th percentile.
- b. Has delayed sleep onset latency defined as self-report of an inability to fall asleep within 30 minutes \geq once a week during the past month.

Cohort 3:

- a. Is absent of neurocognitive impairment defined as performance >10 th percentile on all six measures of attention, memory, and executive functioning.
- b. Has delayed sleep onset latency defined as self-report of an inability to fall asleep within 30 minutes \geq once a week during the past month.

Upon completion of baseline neurocognitive and sleep evaluations, if it is determined that the participant does not have neurocognitive impairment and no delayed sleep onset latency, he or she will not be randomized and will be taken off study.

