4.6 Dose Modifications

There will be no dose modifications for melatonin or placebo. Treatment will be discontinued if a participant reports an adverse event that is not tolerable which the investigator deems related to the study drug. The participant will end treatment on the study and arrangements will be made for the return of unused melatonin/placebo.

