4.7 Concomitant Therapy

Females may take oral contraceptives. If at any time during the six months of study treatment with melatonin/placebo, the participant must start the use of any of the medications listed in the exclusion criteria for medical conditions not present at the time of enrollment, he/she will be taken off-treatment. These medications include: 1) benzodiazepines or other CNS depressants; 2) fluvoxamine; 3) anticoagulants 4) immuno-suppressants or corticosteroids and 5) Nifedipine (Procardia XL)

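### Section 8.1.4 takes participants with unacceptable toxicity off study, and no text keeps the 6-month assessment for people who stop tablets

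*Combined protocol and SAP*

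**What the plan says.** Section 8 carries the heading "CRITERIA FOR REMOVAL FROM PROTOCOL THERAPY AND OFF-STUDY CRITERIA", but only one list follows, the off-study criteria of 8.1. Item 8.1.4 reads "Development of unacceptable toxicity during treatment" and leaves no discretion. Item 8.1.5 lets the principal investigator take someone off study who needs a drug the protocol does not allow.

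Other sections use a different status:

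- **4.6**, on an adverse event that is not tolerable and is judged related to study drug: "The participant will end treatment on the study and arrangements will be made for the return of unused melatonin/placebo".
- **4.7**, on starting an excluded medication: "he/she will be taken off-treatment".
- **7.3**, on missed doses: "Participants will not be removed from the study trial due to poor adherence".
- **10.2** has the monitor check off-study and off-therapy criteria as separate things.

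On the 6-month visit, 6.3 says: "Participants will be scheduled for a return visit to SJCRH within 6 months ± 4 weeks to complete a follow-up evaluation". It goes on to say that the assessment will be timed for while participants are still on melatonin or placebo. For those who cannot travel, it offers a mailed neurocognitive questionnaire and sleep measures. Section 9.2 collects trial-related adverse events up to the 6-month visit.

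**The concern.** Stopping because of toxicity happens after randomisation and can depend on the arm. The primary comparison is a two-sample t-test on change from baseline to 6 months (Protocol Summary, Primary Aim; Section 11.0), so a participant without a 6-month score cannot contribute. Section 11.0 names neither an analysis set nor a method for missing 6-month scores.

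If 8.1.4 ends assessment, people who stop because of side effects leave the comparison, while people who quietly stop taking tablets stay in it under 7.3. What is at stake is the balance that randomisation provides, since a few missing outcomes may be missing for arm-related reasons. The secondary sleep comparison at 3 and 6 months would be affected in the same way.

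**Working it through.** **Text check: what off study appears to end.** The protocol does not define the term. Its other uses are:

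- 8.1.8 applies it when "Study evaluations are complete".
- 3.6 applies it to someone with neither impairment nor delayed sleep onset: "he or she will not be randomized and will be taken off study". Item 8.1.9 repeats this.

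Neither use leaves assessments to come. Read the same way, 8.1.4 would end them. This is an inference.

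**Text check: people who are only off treatment.** Section 6.3 sets the visit for participants generally, and 9.2 presumes a 6-month visit. Both suggest that someone off treatment keeps it. The on-drug timing sentence in 6.3 points the other way. No sentence settles the matter.

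**Text check: the fallback.** The primary outcomes are the six tests named in 3.6: Trail Making B, Digit Span Forward, Digit Span Backward, Controlled Oral Word Association, CVLT-II long delay free recall and CPT-II variability. A mailed questionnaire supplies none of them.

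**Size of the possible bias.** The plan gives no figure to reproduce and no rate of unacceptable toxicity, so this is a range under assumptions.

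Inputs:

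- Arms of 66 and 65 with outcome data (131 in Cohort 2; Secondary Aim 2), and SD 1 for the change score (Primary Aim).
- Two-sided alpha of 0.05/6 = 0.0083 per test, so 0.0083/2 = 0.0042 in the direction of benefit.
- Any drug-related adverse event in the cited 6-month trial of 2 mg: 12% melatonin, 17% placebo (2.2.3).
- Assumed: the share of those events leading to exit (a quarter, with all of them as an extreme case).
- Assumed: gM and gP, how much worse leavers in each arm would have changed than stayers, from 0 to 1 SD.

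Let a and b be the shares leaving the melatonin and placebo arms. The mean among stayers exceeds the full-arm mean by a × gM on melatonin and by b × gP on placebo, so

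bias = a × gM − b × gP (positive favours melatonin).

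SE = √(1/66 + 1/65) = 0.1747. The critical t on 129 df is 2.68. Error rates under no true effect come from the noncentral t with shift bias/SE.

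A quarter of events gives a = 0.12/4 = 0.03 and b = 0.17/4 = 0.0425, or about 2 in 66 and 3 in 65.

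| Exits (a, b) | gM, gP | Bias (SD) | Bias/SE | Two-sided rejection | False claim of benefit |
|---|---|---|---|---|---|
| none | – | 0 | 0 | 0.0083 | 0.0042 |
| 3%, 4.25% | 1, 1 | -0.0125 | -0.07 | 0.0085 | 0.0034 |
| 3%, 4.25% | 1, 0 | +0.03 | +0.17 | 0.0093 | 0.0068 |
| 3%, 4.25% | 0, 1 | -0.0425 | -0.24 | 0.0102 | 0.0020 |
| 12%, 17% | 1, 1 | -0.05 | -0.29 | 0.011 | about 0.002 |
| 12%, 17% | 1, 0 | +0.12 | +0.69 | 0.025 | 0.025 |
| 12%, 17% | 0, 1 | -0.17 | -0.97 | 0.047 | 0.0002 |

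The last three rows suppose that every drug-related event ends participation, which is an extreme case. With gM = gP = 1, exits would have to differ by 17.5 percentage points between arms to shift the result by one standard error (0.1747/1).

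**The case against.** The strongest reply is that this is a wording ambiguity with little behind it. Several parts of that reply stand.

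- **A reader might infer that 4.6 and 8.1.4 flatly contradict each other.** The documents do not support that. An event that is not tolerable (4.6) and unacceptable toxicity (8.1.4) are both undefined and may be different events. They plausibly overlap, and overlapping triggers with different consequences are reason enough to clarify.
- **A reader might infer that the protocol cancels the 6-month visit after toxicity, or bars anyone off tablets from it.** It says neither. The first rests on the ordinary meaning of off study. The second would turn a scheduling sentence in 6.3 into an exclusion.
- **A reader might infer that 8.1.5 conflicts with 4.7.** Item 8.1.5 is discretionary, so both can be followed. Aligning them is tidying.
- **A reader might infer a power shortfall.** None is shown. The Protocol Summary treats 131 as the number with outcome data, after an attrition allowance. Even if a further 10% of the 131 were lost, t-test power for 0.66 at SD 1 and alpha 0.05/6 would be about 81%, against 86% with all 131.
- **A reader might infer that the trial becomes more likely to claim benefit falsely.** The two-sided rates of 0.010 and 0.011 in the table come from bias against melatonin, and there the chance of a false benefit claim falls to about 0.002. It rises only where melatonin leavers would have done sufficiently worse than placebo leavers.

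It is also fair that the cited trial reported no difference between arms in the type or frequency of adverse events, and that the fix may recover few people, because anyone with intolerable effects can still leave on request under 8.1.3. These points limit the size of the problem. They do not explain why toxicity should be the off-study event when poor adherence is not.

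**Conclusion.** The point holds as a cheap improvement, at the lowest severity and with medium confidence. Item 8.1.4 is a stated rule. Read in its ordinary sense, it discards outcomes after randomisation for a reason that may depend on arm, and nothing in 6.3 protects the assessment for people who stop tablets.

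The bias is of unknown size and direction and probably small. If a quarter of the cited 12% and 17% led to exit, it would be between -0.04 and +0.03 SD at the arm-specific extremes, and about -0.01 SD if leavers in both arms would have done 1 SD worse. The chance of a false benefit claim per test would then lie between about 0.002 and 0.007, against 0.0042. The exit share and the 0 to 1 SD range are assumptions. The adverse-event rates come from a different trial with a lower dose. The whole effect depends on 8.1.4 ending the 6-month assessment, which the protocol implies but does not say.

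**What to change.** 1. In Section 8, add an off-treatment list and move 8.1.4 to it. Move need for a disallowed drug (now in 8.1.5) as well, so that it matches 4.7.
2. In Section 8 and in 6.3, state that anyone who stops tablets without withdrawing consent is still asked to complete the 3- and 6-month assessments, whatever 6.3 says about timing them during dosing, and is analysed in the assigned arm.
3. Leave 8.1.3, 8.1.6, 8.1.7 and the rest of 8.1.5 as they are. Participants may always withdraw, and a new cancer or life-threatening illness may make the visit infeasible.

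The cost is wording in two sections and a few visits that are already in the schedule. Keeping people who stopped dilutes the on-treatment effect slightly. If 3% of the melatonin arm stop and gain nothing, the 0.66 target loses 0.66 × 0.03 = 0.02 SD; at 12% it loses 0.66 × 0.12 = 0.08 SD.

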9.0 SAFETY AND ADVERSE EVENT REPORTING REQUIREMENTS

9.1 Reporting Adverse Experiences and Deaths

Principal investigators are responsible for promptly reporting to the IRB any adverse events that are unanticipated, serious, and that may represent potential harm or increased risk to research participants. When an unanticipated death occurs, the PI should report it to the Director of the Office of Human Subjects' Protection immediately, by phone: (██████████), Cell: ██████████, fax: ██████████, or e-mail: [contact].

A reportable event entry into TRACKS should follow within 48 hours. Serious, unanticipated, and related or possibly related events must be reported within 10 working days.

The principal investigator is responsible for reviewing the aggregate toxicity reports and reporting to the IRB if the frequency or severity of serious toxicities exceed those expected as defined in the protocol or based on clinical experience or the published literature. Any proposed changes in the consent form or research procedures resulting from the report are to be prepared by the study team and submitted with the report to the IRB for approval.

The following definitions apply:

A **serious event** refers to any event in which the outcome is fatal or life-threatening, results in permanent disability, causes inpatient hospitalization or prolongs existing inpatient hospitalization, or is a congenital anomaly, cancer, or overdose.

An **unanticipated adverse event** refers to those not identified in their nature, severity, or frequency in the current risk documents (e.g., investigator's brochure), or consistent with the investigational plan.

The following are considered reportable: Any injuries, serious event or other unanticipated adverse events involving risk to participants or others which occur at a frequency above that considered acceptable by the investigators and the IRB. (FDA) As described in 4.3 above, the OHSP Director or designee performs the initial review of unanticipated problems or serious adverse event reports. Internal reports of events that are unanticipated, serious, and related or possibly related to study interventions or procedures are then forwarded to the IRB Chair or designee and if necessary, referred to the full IRB. Based on the frequency and seriousness of adverse events, the IRB Chair or Committee may deem it necessary to suspend or terminate a research study or studies.

All anticipated Grade III or IV adverse events will be reported to the IRB in the continuing review report and/or summary. The DSMB will monitor accrual and toxicities every six months.

9.2 Recording Adverse Events and Serious Adverse Events

All serious adverse events will be recorded in the source, database and/or case report form. Adverse events unrelated to the trial will not be recorded unless they are grade III or above (CTCAEv4). Adverse events that are related to the trial will be captured in the source document, database and/or case report form. Adverse events related to the trial will be collected until the time of the participant's six month follow-up visit.

10.0 DATA COLLECTION, STUDY MONITORING, & CONFIDENTIALITY

10.1 Data Collection

Data for this study will be managed by the Neuropsychology Research Team and the Clinical and Survey Research Center in the Department of Epidemiology and Cancer Control. Data collected at baseline and follow-up assessments will be entered by optical scanning. The optical scanning program has the capacity for designer specific error checks, flagged at the time the questionnaires are scanned. After data are scanned, they are processed and converted into a SAS (Cary, NC) format where a second error check is completed. Data from neurocognitive tests are double-

entered into a separate secure Access database and compared for accuracy. Data from biological specimens will be transmitted to the survey research center with a secure file transport protocol, double-entered and compared for accuracy. All data mismatches will be reviewed by two members of the survey center staff and compared to the original documents (when applicable) for resolution. Actigraphy and MEMS cap data will be downloaded using software provided by the product manufacturers and processed with published coding algorithms.

10.2 Study Monitoring

Source document verification of eligibility for all SJCRH cases will be performed within two weeks of completion of enrollment. This will include verification of appropriate documentation of consent. Monitoring of timeliness of serious adverse event reporting will be done as events are reported in TRACKS.

Monitoring of this protocol is considered to be in the “moderate” risk category. The Monitoring Plan is outlined in a separate document from this protocol, but has been submitted for review and approval by the Clinical Trials Scientific Review Committee and the Institutional Review Board (IRB).

The study team will hold monthly meetings and review case histories or quality summaries on participants. Source document verification of eligibility and informed consent for 100% of St. Jude participants will be performed by the Eligibility Coordinators within 10 working days of completion of enrollment. The Clinical Research Monitor will perform monitoring of applicable essential regulatory documentation. Also, reviewing for the timeliness of serious adverse event reporting (type, grade, attribution, duration, timeliness and appropriateness) for selected study participants *semi-annually* and track accrual continuously. The monitor will verify those data points relating to the primary study objective for a certain number of study enrollees as specified in the Moderate Risk monitoring plan checklist for this study. Protocol compliance monitoring will include participant status, safety assessments, eligibility, the informed consent process, participant protocol status, off-study, and off-therapy criteria. The Monitor will generate a formal report which is shared with the Principal Investigator (PI), study team and the Internal Monitoring Committee (IMC).

The DSMB will monitor the study every 6 months.

Monitoring may be conducted more frequently if deemed necessary by the CPDMO or the IMC. Continuing reviews by the IRB and CT-SRC will occur at least annually. In addition, SAE reports in TRACKS (Total Research and Knowledge System) are reviewed in a timely manner by the IRB/ OHSP.

10.3 Confidentiality

All study information will be stored in locked research files and password protected databases. Any information learned from this study in which the subject might be identified will be confidential and disclosed only with the subject's permission. Publications will present the results in such a way as to make it impossible to identify individuals. Upon agreeing to participate, the consent form and Health Insurance Portability and Accountability ACT (HIPAA) compliance form will be signed by the participant and the principal investigator or designee.

11.0 STATISTICAL CONSIDERATIONS

The primary focus of this study is to evaluate the efficacy of melatonin on neurocognitive functioning in long term survivors of childhood cancer. Currently, there are 2,331 survivors potentially eligible for this study and 1,410 (61% have been identified as expected to have least one area of neurocognitive impairment. Further, it is estimated that among all the eligible survivors roughly 30% will have delayed sleep (sleep onset latency ≥ 30 minutes). Thus, the eligible survivors can be classified into three distinct cohorts (I) Those who are neurocognitively impaired but don't have delayed sleep 987 (II) Those who are neurocognitively impaired and have delayed sleep 423, i.e. 30% of 1,410, and (III) Those who don't have neurocognitive impairment but have delayed sleep problems (this would be roughly 30% (276) of those who are not neurocognitively impaired. Targeted enrollment for the study is 987 survivors and expected evaluable is 395.

[figure not shown]

Figure 2. Three group stratification with parallel allocation to melatonin/placebo

Primary Objective: Examine the efficacy of melatonin treatment on neurocognitive functioning in adult survivors of childhood cancer.

- Hypothesis 1: Long-term survivors of childhood cancer with documented baseline neurocognitive deficits (Cohorts 1 and 2), in attention, memory,

and/or executive functioning, randomized to the melatonin treatment arm, will demonstrate improved neurocognitive performance following six months of treatment compared to those randomized to placebo.

The primary objective of this study is to demonstrate that treatment with melatonin will be associated with improvement in neurocognitive performance. This will be evaluated in Cohorts 1 and 2 independently. The study will be conducted by randomizing survivors to melatonin or placebo within each of the two Cohorts.

For those who are in Cohorts 1 and 2 baseline neurocognitive evaluation along with other evaluations will be obtained prior to randomization to melatonin or placebo arm. After randomization, sleep data will be collected using actigraphy in week one when the survivors are in their homes. The intervention will be delivered for a period of six months with regular phone calls for monitoring. Then one week before the six month visit sleep data using actigraphy will be collected. The neurocognitive data will be collected at the 6 month return visit (post-treatment).

There are 10 subscales on which a survivor could be impaired and, out of 10 such subscales, we have identified six in which the marginal impairment rates were seen to be greater than 15%. There are normalized Z-scores available for each subscale and a survivor that falls below the 10% (≤ -1.3) is classified as impaired on that subscale. It is possible that a survivor could be impaired on more than one subscale but we will assess improvement in each subscale independently. Thus, we will have the Z-score corresponding to each of the subscales within at baseline and at follow-up visit. For simplicity, consider the first subscale. We don't expect to see any change in the Z-scores for the placebo arm but we do expect to see an improvement in the melatonin arm. Let Z_{1m}^1 and Z_{2m}^1 denote the Z-scores at baseline and follow-up time points for the first subscale on melatonin arm and let Z_{1p}^1 and Z_{2p}^1 denote the Z-scores at baseline and follow-up time points for the first subscale in the placebo arm. Let $Z_{DM}^1 = Z_{2m}^1 - Z_{1m}^1$ and $Z_{DP}^1 = Z_{2p}^1 - Z_{1p}^1$ denote the difference between the two time points in the two arms. Then our interest is in testing the null hypothesis $H_0: \mu_{Z_{DM}^1} = \mu_{Z_{DP}^1}$ vs $H_1: \mu_{Z_{DM}^1} \neq \mu_{Z_{DP}^1}$ i.e. the mean of the difference scores for the first subscale would be same for the two arms vs. they will be different. The lowest test-retest correlation coefficient for the neurocognitive measures has been observed to be 0.60. Then, assuming the difference in the Z-scores to be normally distributed but assuming (conservatively) the variance to be 1, we will need to randomize 131 survivors between the melatonin and placebo arm to detect an improvement of 0.66 units (in standardized scale, considered to be clinically meaningful) with 80% power with type I error control $\alpha=0.05/6=0.0083$ to adjust for multiplicity of 6 tests for each subscale. However, the sample size required to evaluate the secondary objective in cohorts 2 and 3 is 131 and 133, respectively, per cohort. Thus, we plan to enroll 131 research participants from Cohorts 1 and 2 and 133 research participants from Cohort 3.

In addition to analyzing the differences for each subscale we will also analyze the data in an alternative manner as follows. For each subscale an improvement will be defined if the difference in the Z-score (follow-up time point – baseline) is greater than 0.6 units (≥ 0.6). Let us assume that the probability of observing an improvement in a subscale in an individual in the placebo group is about 5% and then the total of 6 subscales (assuming them to be independent with the same probability of improvement) will follow a Binomial distribution $B(6, 0.05)$ with a mean of 0.3 and SD of 0.54. If we assume that the probability of improvement to be higher say about 12% in the melatonin group then the total score in that group will follow a Binomial distribution $B(6, 0.12)$ with a mean of 0.72 and SD of 0.80. Then, we will use two-sample Behrens-Fisher t-statistic to compare the two means. With a sample size of between 65 and 67 in each group we will have roughly 90% power to detect a difference of 0.42 units with type I error control $\alpha=0.05$.

Secondary Objective: Evaluate the efficacy of melatonin treatment on delayed sleep onset latency in long-term childhood cancer survivors.

- Hypothesis 2: Long-term survivors of childhood cancer with delayed sleep onset latency at baseline (Cohorts 2 and 3), randomized to the melatonin treatment arm, will demonstrate improved sleep onset latency following six months of treatment compared to the placebo groups.

The primary interest of Objective 2 is to assess the efficacy of melatonin on delayed sleep onset latency in adult survivors of childhood cancer, which will be evaluated in Cohorts 2 and 3. We hypothesize that survivors randomized to the melatonin treatment arm will evidence a greater improvement in sleep onset latency compared to survivors randomized to placebo. The CCSS cohort mean and SD for sleep onset latency among participants with delayed sleep onset latency (i.e. $SOL \geq 30$ minutes) is 46.2 and 27.7 minutes, respectively. The test-retest correlation for sleep onset latency from the PSQI has been observed to be in the range of 0.70. Following the justification set forth in Aim 1, and assuming the SD to be 27.7, we will need to randomize 131 and 133 survivors between the melatonin and placebo arms in Cohort 2 and Cohort 3, respectively, to see an improvement of 15 minutes in sleep onset latency with 80% power with type I error control $\alpha=0.05$. The analysis for Aim 2 will be completed using a two-sample t-test.

Secondary Objective: Investigate whether improvement in sleep onset latency due to melatonin treatment is associated with neurocognitive improvement in long-term childhood cancer survivors.

- Hypothesis 3: Improvement in sleep onset latency with melatonin treatment will result in improved neurocognitive performance in long-term childhood cancer survivors who have both comorbid sleep onset latency and neurocognitive deficits at baseline (Cohort 2).

The secondary interest of Objective 2 is to investigate the association between

sleep onset latency and specific neurocognitive processes in survivors with comorbid sleep and neurocognitive dysfunction [Cohort 2]. We hypothesize that decreased sleep onset latency following 6 months of melatonin treatment will be associated with improved neurocognitive performance. With a sample size of 131 in Cohort 2 [66 randomized to melatonin, 65 randomized to placebo] we will have 80% power to detect a correlation of at least 0.25 between reduced sleep onset latency and improved neurocognitive performance with type 1 error control $\alpha=0.05$.

Exploratory Objective: Explore the association between endogenous melatonin levels and improvement in sleep onset latency.

- Exploratory Hypothesis 1: Improvement in sleep onset latency following melatonin treatment will be independent of baseline endogenous melatonin levels.

Linear regression model and/or logistic regression model will be used to evaluate the association between serum melatonin and improvement in sleep.

Exploratory Objective: Explore the association between sleep quality and health-related quality of life and distress.

- Exploratory Hypothesis 3: Improved sleep quality will be associated with decreased psychological distress and enhanced quality of life.

Once again regression approaches, as discussed above, will be utilized to evaluate the association between sleep quality and health-related quality of life and psychological distress.

